12.1 Nivolumab³⁰

12.1.1 Other Names

Additional names for nivolumab include [REDACTED].

12.1.2 Classification

Anti-PD-1MAB

12.1.3 Mode of Action

Nivolumab is a fully human monoclonal immunoglobulin (Ig) G4 antibody that binds to the PD-1 cell surface membrane receptor, a negative regulatory molecule expressed by activated T and B lymphocytes. Inhibition of the interaction between PD-1 and its ligands promotes immune responses and antigen-specific T cell responses to both foreign antigens as well as self-antigens.

12.1.4 Description

Nivolumab Injection, 100 mg/vial (10 mg/mL) is a clear to opalescent, colorless to pale, yellow liquid, light (few) particulates may be present. [REDACTED]

Open-label cartons will be supplied with 5 vials per carton.

12.1.5 Preparation and Administration

Nivolumab injection should be diluted with 0.9% Sodium Chloride Injection, USP or 5% Dextrose Injection, USP to protein concentrations as low as .35 mg/mL. During drug product preparation and handling, vigorous mixing or shaking is to be avoided. Care must be taken to assure sterility of the prepared solution as the product does not contain any anti-microbial preservative or bacteriostatic agent. No incompatibilities between nivolumab and polyolefin bags have been observed.

Nivolumab is to be administered as an approximately 60 minute IV infusion, using a volumetric pump with a 0.2/0.22 micron in-line filter at the protocol-specified dose. It is not to be administered as an IV push or bolus injection. At the end of the infusion, flush the line with a sufficient quantity of normal saline.

NOTE: Cohort 1 patients received nivolumab over 30 minute IV infusion. A few mild infusion reactions occurred on Cohort 2 with the nivolumab infusion, requiring only steroids and resuming dose at 50%. Infusion time increased to 60 minutes per package insert guidelines.

12.1.6 Storage and Stability

Clinical supplies must be stored in a secure, limited-access location. Nivolumab vials must be stored at a temperature of 2°C to 8°C and should be protected from light and freezing. If stored in a glass front refrigerator, vials should be stored in the carton. Receipt and dispensing of trial medication must be recorded by an authorized person at the trial site.

The administration of nivolumab infusion must be completed within 24 hours of preparation. If not used immediately, the infusion solution may be stored under refrigeration conditions (2°-8°C, 36°-46°F) for up to 24 hours, and a maximum of 8 hours of the total 24 hours can be at room temperature (20°-25°C, 68°-77°F) and room light. The maximum 8-hour period under room temperature and room light conditions includes the product administration period.

12.1.7 Drug Interactions

No formal pharmacokinetic drug-drug interaction studies have been conducted with nivolumab.

Nivolumab is not expected to have any effect on cytochrome P450 or other drug metabolizing enzymes in terms of inhibition or induction, and is, therefore, not expected to induce these types of PK-based drug interactions.

12.1.8 Agent Availability

Nivolumab will be supplied by BMS.

The initial supply of nivolumab will be sent directly to the site upon site activation. As needed, nivolumab may be requested by the principal investigator (or their authorized designees) at each participating institution. The investigator, or a responsible party designated by the investigator, must maintain a careful record of the receipt, disposition, and return/destruction (site's drug destruction policy must be reviewed and approved by PrECOG before any study drug can be destroyed at a site) of nivolumab.

12.1.9 Agent Ordering

PrECOG will be responsible for ordering drug for re-supply to the site. Requests for shipments of nivolumab will be coordinated between PrECOG and BMS.

12.1.10 Agent Accountability

Nivolumab will be stored in a secure location. Only authorized pharmacy and study staff will have access to this agent. Drug accountability will be performed by PrECOG.

12.1.11 Side Effects

The overall safety experience with nivolumab is based on approximately 1500 subjects as either a monotherapy or in combination with other therapeutics. In general for monotherapy, the safety profile is similar across tumor types. The one exception is pulmonary inflammation AEs which may be numerically greater in subjects with Non-Small Cell Lung Cancer possibly because in some cases it can be difficult to distinguish between nivolumab-related and unrelated causes of pulmonary symptoms and radiographic changes. The most frequently reported treatment related AE is fatigue which is almost always low grade.

Most related AEs are thought to be due to the effects of inflammatory cells on specific tissues. The most common treatment-related adverse events seen in clinical trials of nivolumab included rash, pruritus, cough, peripheral edema, fatigue, arthralgias, upper respiratory tract infections, diarrhea and liver function test abnormalities. Additionally a number of patients experienced more severe autoimmune effects including immune-mediated pneumonitis, immune-mediated colitis, immune-mediated hepatitis, immune-mediated nephritis, immune-mediated encephalitis and immune-mediated endocrinopathies, such as adrenal insufficiency, hypothyroidism/hyperthyroidism and Type I Diabetes Mellitus. Less than 1% of patients in clinical trials experienced severe infusion reactions.

Nivolumab is a Pregnancy Category D drug.

Please refer to the Nivolumab IB and commercial package insert for full prescribing information.

12.2 Lirilumab³⁷

12.2.1 Other Names

[REDACTED]

12.2.2 Mode of Action

Lirilumab is a fully human immunoglobulin (Ig) G4 monoclonal antibody (mAb) that is specific for a subset of human killer cell immunoglobulin-like receptors (KIRs). KIRs bind their cognate ligands and then transmit inhibitory or activating signals that determine the activational state of NK cells. The binding of inhibitory KIRs to their human leukocyte antigen (HLA) ligands keeps the NK cell quiescent.

[REDACTED]

12.2.3 Description

[REDACTED]

12.2.4 Preparation and Administration

[REDACTED]

12.2.5 Storage and Stability

[REDACTED]

[REDACTED]

12.2.6 Drug Interactions

12.2.7 Agent Availability

Lirilumab will be supplied by BMS.

The initial supply of lirilumab will be sent directly to the site upon site activation. As needed, lirilumab may be requested by the principal investigator (or their authorized designees) at each participating institution. The investigator, or a responsible party designated by the investigator, must maintain a careful record of the receipt, disposition, and return/destruction (site's drug destruction policy must be reviewed and approved by PrECOG before any study drug can be destroyed at a site) of lirilumab.

[figure not shown]
12.2.8 Agent Ordering

PrECOG will be responsible for ordering drug for re-supply to the site. Requests for shipments of lirilumab will be coordinated between PrECOG and BMS.

12.2.9 Agent Accountability

Lirilumab will be stored in a secure location. Only authorized pharmacy and study staff will have access to this agent. Drug accountability will be performed by PrECOG.

12.2.10 Side Effects

Please refer to the Lirilumab IB for details.

13. Statistical Considerations

13.1 Study Design & Sample Size Considerations

This is a Phase Ib study evaluating whether the addition of lirilumab to nivolumab is feasible and safe in patients that are either cisplatin-ineligible or refuse cisplatin-based chemotherapy and have muscle-invasive urothelial carcinoma of the bladder in the neoadjuvant therapy setting. Eligible patients will be assigned sequentially to either nivolumab monotherapy in Cohort 1, and if there is no negative safety signal (see next paragraph) after the first 12 patients, subsequent patients will be assigned to Cohort 2 treated with nivolumab/lirilumab.

13.1.1 Interim Safety Analysis (Primary Endpoint)

Treatment-related toxicities as noted below related to nivolumab or nivolumab/lirilumab will be monitored in each cohort of the study separately after 6 and 12 patients in Cohort 1 and 6 patients in Cohort 2 have completed surgery. There will be no suspension to accrual.

- Any Grade hypophysitis, meningitis, or immune-related neurologic AEs
- Grade 2 or higher myocarditis
- Persistent Grade 2 immunologic AEs (such as colitis, pneumonitis, and nephritis) that do not recover to Grade 1 or resolve within 6 weeks after the last dose of study drug (Exceptions: rash, fatigue, amylase/lipase elevations, other electrolyte abnormalities).
- Grade 3 or higher immunologic AEs such as uveitis, pericarditis, hepatitis, colitis/diarrhea, nephritis, pancreatitis, myositis, endocrine, rash, etc., except for Grade 3 hypothyroidism, Grade 3 pruritus or Grade 3 infusion reaction.
- Grade 4 non immunologic AEs, as well as Grade 4 hypothyroidism or Grade 4 infusion reaction.

If 3 or more of these 6 patients on a single cohort experience treatment-related adverse events as noted above related to nivolumab or nivolumab/lirilumab, the study will be suspended for a safety review. The following table gives the probabilities of stopping given various probabilities of toxicity.

True but unknown probability of immunologic toxicity	0.17	0.25	0.33	0.42	0.5
Probability of suspension	0.06	0.17	0.32	0.49	0.66

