5.4 Interim Safety Analysis

After 6 and 12 patients on Cohort 1 and 6 patients on Cohort 2 complete surgery, the study will be monitored for nivolumab or nivolumab/lirilumab treatment-related toxicities as noted below.

- Any Grade hypophysitis, meningitis, or immune-related neurologic AEs

- Grade 2 or higher myocarditis
- Persistent Grade 2 immunologic AEs (such as colitis, pneumonitis, and nephritis) that do not recover to Grade 1 or resolve within 6 weeks after the last dose of study drug (Exceptions: rash, fatigue, amylase/lipase elevations, other electrolyte abnormalities).
- Grade 3 or higher immunologic AEs such as uveitis, pericarditis, hepatitis, colitis/diarrhea, nephritis, pancreatitis, myositis, endocrine, rash, etc., except Grade 3 hypothyroidism or Grade 3 infusion reaction.
- Grade 4 non immunologic AEs, as well as Grade 4 hypothyroidism or Grade 4 infusion reaction.

There will be no suspension to accrual after the first 6 patients in each cohort. Also, accrual will start on Cohort 2 once accrual to Cohort 1 is complete (unless needed based on toxicity noted).

If 3 or more of these 6 patients on a single cohort experience nivolumab or nivolumab/lirilumab treatment-related adverse events as noted above, the study will be suspended for a safety review.

6. Treatment Plan

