#### **7.8. Interim Analysis**

There will be 3 interim safety analyses in this study. After 6 and 12 patients on Cohort 1 and 6 patients on Cohort 2 complete surgery, the study will be monitored for nivolumab or nivolumab/lirilumab treatment-related toxicities as noted below.

- Any Grade hypophysitis, meningitis, or immune-related neurologic AEs
- Grade 2 or higher myocarditis
- Persistent Grade 2 immunologic AEs (such as colitis, pneumonitis, and nephritis) that do not recover to Grade 1 or resolve within 6 weeks after the last dose of study drug (Exceptions: rash, fatigue, amylase/lipase elevations, other electrolyte abnormalities).
- Grade 3 or higher immunologic AEs such as uveitis, pericarditis, hepatitis, colitis/diarrhea, nephritis, pancreatitis, myositis, endocrine, rash, etc., except Grade 3 hypothyroidism or Grade 3 infusion reaction.
- Grade 4 non immunologic AEs, as well as Grade 4 hypothyroidism or Grade 4 infusion reaction.

The first interim safety analysis will be performed as soon as the 6th patient in cohort 1 complete radical cystectomy (RC) surgery. A treatment-related AE by toxicity grade and SOC summary tables will be provided to clinical team review to determine whether 3 or more patients meet above specified AEs. If 3 or more patients are identified, the study will be suspended for a safety review.

An AE listing will also be provided for clinical team review.

The 2nd interim safety analysis will be performed as soon as the 12th patient in cohort 1 complete RC surgery. The same AE analysis as the first interim analysis will be performed for the all 12 patients. If 6 or more patients experience above specified AEs, the study will be suspended for a safety review.

The 3rd interim safety analysis will be performed as soon as the 6th patient in cohort 2 complete RC surgery. The same AE analysis will be repeated for the all 18 patients. If 9 or more patients experience above specified AEs, the study will be suspended for a safety review.

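### The suspension-probability table is correct for one look at 6 patients, but it is unlabelled and does not describe the Cohort 1 looks at 6 and 12 or the SAP's pooled Cohort 2 look

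*Protocol*

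**What the plan says.** Protocol 13.1.1 states that toxicity "will be monitored in each cohort of the study separately after 6 and 12 patients in Cohort 1 and 6 patients in Cohort 2"; a patient counts towards a look once surgery is done. The only boundary it gives is "If 3 or more of these 6 patients on a single cohort experience treatment-related adverse events as noted above", which leads to suspension for a safety review. Protocol 5.4 has the same schedule and the same single boundary: "If 3 or more of these 6 patients on a single cohort experience nivolumab or nivolumab/lirilumab treatment-related adverse events as noted above". Neither section gives a count for 12 patients.

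Protocol 13.1 allows assignment to Cohort 2 if there is no negative safety signal after the first 12 patients, and refers to the paragraph that follows for what that means. That paragraph is 13.1.1.

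Directly after the 3-of-6 rule comes the sentence "The following table gives the probabilities of stopping given various probabilities of toxicity" and a two-row table:

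| Row | | | | | |
|---|---|---|---|---|---|
| "True but unknown probability of immunologic toxicity" | 0.17 | 0.25 | 0.33 | 0.42 | 0.5 |
| Second row: "Probability of suspension" | 0.06 | 0.17 | 0.32 | 0.49 | 0.66 |

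The table does not say which look or which cohort it covers.

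SAP 7.8 lists three looks, each with a boundary. The first is 3 or more of 6 in Cohort 1. The second covers all 12 Cohort 1 patients: "If 6 or more patients experience above specified AEs, the study will be suspended for a safety review". The third comes after 6 Cohort 2 patients and covers all 18 patients, with a trigger of 9 or more. The SAP gives no operating characteristics for any look. Its section 8 says there are no departures from the protocol's analyses.

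**The concern.** The table is the only stated operating characteristic of the trial's only numerical safety rule. A reader who takes it as the chance that a given toxicity rate suspends the study will apply it to Cohort 1. That cohort has two opportunities to suspend, so its cumulative probability depends on the 12-patient boundary as well.

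That boundary is not in the protocol, which is the document investigators and ethics boards work from, yet the protocol ties the step from monotherapy to the combination to the 12-patient look. For Cohort 2 the two documents state different rules, so the table cannot describe both. At stake is whether the people overseeing the trial know how sensitive the rule is, and whether they would apply the same rule.

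**Working it through.** **Inputs.** The looks and the 3-of-6 boundary come from protocol 5.4 and 13.1.1. The 6-of-12 and 9-of-18 boundaries come from SAP 7.8. The true rates are the table's headings, read as 2/12, 3/12, 4/12, 5/12 and 6/12 rounded to two decimals. Patients are taken as independent with a common toxicity rate p.

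**Step 1: reproduce the table.** For one look at 6 patients,

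P(X ≥ 3 | n = 6) = 1 − Σ over x = 0 to 2 of C(6,x) pˣ (1−p)⁶⁻ˣ.

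The results are 0.062, 0.169, 0.320, 0.490 and 0.656, which round to all five printed values. With the printed decimals instead of twelfths the results are 0.066, 0.169, 0.313, 0.497 and 0.656, so twelfths are evidently what was used.

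**Step 2: add the second Cohort 1 look under the SAP boundary.** Let X be the number of events in the first six patients and Y the number in the second six. The study is suspended if X ≥ 3, or if X ≤ 2 and X + Y ≥ 6:

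P(suspend) = P(X ≥ 3) + Σ over x = 0 to 2 of P(X = x) · P(Y ≥ 6 − x).

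At p = 1/2:
- P(X ≥ 3) = 42/64 = 0.656
- x = 0: (1/64)(1/64) = 1/4096
- x = 1: (6/64)(7/64) = 42/4096
- x = 2: (15/64)(22/64) = 330/4096
- added by the second look: 373/4096 = 0.091
- total: 0.747

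All five rates:

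| True rate | Table | One look, recomputed | Two looks (3/6, then 6/12) | Added by second look |
|---|---|---|---|---|
| 2/12 | 0.06 | 0.062 | 0.064 | 0.002 |
| 3/12 | 0.17 | 0.169 | 0.182 | 0.013 |
| 4/12 | 0.32 | 0.320 | 0.357 | 0.038 |
| 5/12 | 0.49 | 0.490 | 0.560 | 0.070 |
| 6/12 | 0.66 | 0.656 | 0.747 | 0.091 |

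**Step 3: Cohort 2.** Under the protocol there is one look at 6 with a boundary of 3, so the table applies as printed. Under SAP 7.8 the trigger is 9 events among 18. If Cohort 1 passed its second look without suspension it had at most 5 events, so Cohort 2 needs at least 9 − 5 = 4 events among 6. If Cohort 1 had 2 or fewer events, the trigger cannot be reached even if all six Cohort 2 patients have events, because 2 + 6 = 8. In the most sensitive case (5 Cohort 1 events), the chance that the third look triggers is P(X ≥ 4 | n = 6) = 0.009, 0.038, 0.100, 0.203 and 0.344 at the five rates. The table shows 0.06, 0.17, 0.32, 0.49 and 0.66.

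**The case against.** The strongest reply is that nothing in the table is miscalculated. It follows the 3-of-6 sentence and gives the probabilities for that rule. A reader might infer from the two-look schedule that the printed values are wrong; the documents do not support that, because all five reproduce. For Cohort 2 under the protocol they are also complete.

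On the protocol alone, the numerical trigger can be read as applying only to the first six patients of each cohort, with the 12-patient look a review without a count. The table would then be Cohort 1's suspension probability as well. The wording allows this reading, but it leaves the 12-patient condition in 13.1 without a numerical criterion.

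A reader might also infer that the plan has no rule at 12 patients. It has one, in SAP 7.8, and SAP 2.1 says the SAP supersedes the protocol's statistical considerations. The same paragraph says substantial differences will be identified, however, and section 8 identifies none.

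Much larger gaps appear if one supposes 3 of 12 at the second look, or 3 of 6 applied afresh to the second six. The first has no basis in the text. The second conflicts with the SAP, which assesses all 12 patients together. Neither should be used to size this point.

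Finally, the gap under the documented rule is small at low toxicity rates, and the consequence is suspension for review, not closure. Both observations stand. Protocol 5.4 also lets Cohort 2 accrual begin when Cohort 1 accrual is complete, so the 12-patient look may in practice bear on continuing Cohort 2 more than on opening it. That does not supply the missing count.

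**Conclusion.** The point holds as one of incomplete labelling and of disagreement between protocol and SAP. It is not an arithmetic error. The table correctly describes one look at 6 patients with a boundary of 3.

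As a description of Cohort 1 under the only two-look rule written down, it understates the cumulative probability of suspension by less than 2 points up to a 25% toxicity rate, and by about 4, 7 and 9 points at 33%, 42% and 50%. As a description of Cohort 2, it fits the protocol's single-cohort rule but not the SAP's pooled one, which is harder to trigger when Cohort 1 has passed its own looks.

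The figures assume independent patients with a common rate, the SAP boundaries for Cohort 1, and that suspension at either look counts as the event. The Cohort 2 comparison also assumes that Cohort 1 was not suspended. On the protocol alone, no two-look figure can be computed for Cohort 1, because the second boundary is not stated. This should be corrected, but it does not undermine the design.

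**What to change.** 1. Reconcile protocol 5.4 and 13.1.1 with SAP 7.8 so that every look has one agreed boundary, stated identically in both documents. This covers the count at 12 patients in Cohort 1 and whether the Cohort 2 look is judged within the cohort or pooled over 18. Which rule to adopt is for the sponsor and the investigators to decide.
2. Label the existing row of the table as one look at n = 6 with a boundary of 3.
3. Add a row of cumulative Cohort 1 probabilities over both looks (0.06, 0.18, 0.36, 0.56, 0.75 if 6 of 12 is kept), and a row for the reconciled Cohort 2 rule.
4. Correct SAP section 8 to record any boundary that still differs from, or adds to, the protocol.

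The cost is a sentence and two table rows, plus the correction to SAP section 8. No patients or data are added. If the SAP boundaries for Cohort 1 are kept, the stated Cohort 1 suspension probabilities become slightly higher.

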13.2 Statistical Analysis

13.2.1 Primary Objective

The primary endpoint of this study is the rate of Grade 3 or higher adverse events during neoadjuvant treatment.

13.2.1.1 Analytic Plan for Primary Objective

The rates of Grade 3 or higher adverse events during neoadjuvant treatment will be reported along with 90% exact binomial confidence intervals. In Cohort 1 the maximum width of the confidence interval is 0.51 while in Cohort 2 it is 0.36.

13.2.2 Key Secondary Objective

The key secondary endpoint of this study is the change in tumor-infiltrating CD8+ T-cell density from TURBT to radical cystectomy in each arm. CD8+ TIL density is defined as the number of CD8+ tumor infiltrating T-cells per 100 tumor cells within a 400x HPF. All biopsies will be reviewed centrally by a pathologist. Final CD8+ T-cell density for each patient will be the mean of five representative tumor fields in a cystectomy sample with the greatest gross percentage of tumor infiltrating lymphocytes (minimum 100 tumor cells per representative field), as selected by the pathologist. The mean change in CD8+ TIL density of each cohort will be calculated by averaging the change in TIL densities of all patients in the cohort. (Additionally, the TIL density at radical cystectomy will be compared between the two cohorts as one of the exploratory objectives).

13.2.2.1 Analytic Plan for Key Secondary Objective

The estimate of the standard deviation of tumor-infiltrating CD8+ T-cell density in urothelial carcinoma (defined as CD8+ TILs/ 100 tumor cells in high power field [HPF]) is derived from a prior study published by Sharma et al. In that cohort of 69 patients who underwent cystectomy, the standard deviation of TIL density was 3.9.¹² Our hypothesis is that the change in TIL density between TURBT and radical cystectomy will be approximately 3.0 CD8+ TILs per 100 tumor cells within HPF. Up to 43 patients will be enrolled for 36 eligible, treated patients (12 on nivolumab monotherapy and 24 patients on the combination). In each cohort a one-sample Wilcoxon signed-rank test will be used to test whether the mean change in TIL density differs significantly from zero. In the monotherapy cohort there will be 81% power to detect the hypothesized difference with a one-sided type I error rate of 0.05. In the combination cohort there will be 98% power to detect the hypothesized difference with a one-sided type I error rate of 0.05. Additionally, the TIL density at radical cystectomy will be compared between the two cohorts using a Wilcoxon rank sum test. With this design there is 82% power to detect a difference of 0.80 standard deviations, which translates to a difference of about 3.0 TILs per 100 tumor cells, between the two cohorts with a one-sided type I error rate of 0.1. This comparison will be exploratory in nature.

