#### **7.7.1. The mean change of CD8+ TIL density in each cohort**

There are 2 CD8+ TIL density readings for each patient. One is prior and another one is after study treatment. Patients obtained prior treatment CD8+ TIL density from TURBT. Patients obtained post treatment CD8+ TIL density from radical cystectomy. The mean change in CD8+ TIL density of each cohort will be calculated by averaging the change in TIL densities of all patients in the cohort.

In each cohort a one-sample Wilcoxon signed-rank test will be used to test whether the mean change in TIL density differs significantly from zero. This is key secondary objective (SAP section 7.4.2.1).

Additionally, the TIL density at radical cystectomy (post study treatment) will be compared between the two cohorts using a Wilcoxon rank sum test. This is the first exploratory objective (SAP section 7.4.3.1).

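### The exploratory between-cohort comparison of cystectomy TIL density is unadjusted, although the cohorts are non-randomised and a TURBT density is planned for every patient

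*Protocol*

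**What the plan says.** Protocol 13.2.2.1 first tests the within-cohort change in CD8+ TIL density with a signed-rank test. It then adds a comparison between cohorts: "Additionally, the TIL density at radical cystectomy will be compared between the two cohorts using a Wilcoxon rank sum test". The power statement reads "With this design there is 82% power to detect a difference of 0.80 standard deviations". The protocol equates that effect with roughly 3.0 TILs per 100 and sets the level at 0.1, one-sided. It labels this comparison exploratory.

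SAP 7.7.1 keeps the same test: "the TIL density at radical cystectomy (post study treatment) will be compared between the two cohorts using a Wilcoxon rank sum test". It ties it to the first exploratory objective (SAP 7.4.3.1, which names no test). SAP 7.4.2.1 also lists it inside the key secondary analytic plan, without the exploratory label. No covariate, stratification or change score enters the test anywhere.

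Two design facts bear on this.
- Allocation is by order of entry (protocol 13.1): "Eligible patients will be assigned sequentially". Cohort 1 (12 patients) fills before Cohort 2 (24 patients).
- The baseline value is planned for everyone. Tissue is mandatory at baseline and at cystectomy (protocol 4.4), the counting method is the same at both times (protocol 14.1.2), and SAP 7.7.1 says "There are 2 CD8+ TIL density readings for each patient".

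The TURBT value is used elsewhere: in the within-cohort change, and in a secondary between-cohort rank-sum comparison of percent change (protocol 13.2.3.1 item 1; SAP 7.4.2.2 and 7.7.2).

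**The concern.** The cohorts are compared on the post-treatment value alone. Without randomisation, pre-treatment densities may differ between them systematically as well as by chance. Whatever part of a baseline difference persists to cystectomy is then read as a lirilumab effect, or hides one. The variation that baseline explains also stays in the error term and costs power in a comparison of 12 with 24 patients.

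This is the only between-cohort TIL comparison on the absolute density scale, and the only one with a stated power. It is therefore likely to be cited when the results are used to judge what lirilumab adds.

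**Working it through.** **Inputs.** From protocol 13.2.2.1: 12 and 24 patients, effect 0.80 SD, one-sided level 0.10, and SD from a published cystectomy series ("the standard deviation of TIL density was 3.9"). The pre/post correlation ρ is not in the documents, so it is varied over 0, 0.3, 0.5 and 0.7. Normal data with equal pre and post SD are assumed, and all 36 patients are assumed to have both readings.

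**1. The plan's own figure.** A noncentral t calculation with both group sizes scaled by the Wilcoxon efficiency 3/π gives 81.6%. Simulation with the exact rank-sum critical value gives about 81%. The stated 82% stands. On the raw scale, 0.80 × 3.9 = 3.12, consistent with about 3.0.

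**2. Size of a chance baseline imbalance.** SE of the baseline difference = √(1/12 + 1/24) = 0.354 SD, and 0.354 × 3.9 = 1.38 TILs per 100 tumor cells. The probability of a chance imbalance beyond 0.5 SD in either direction is 2 × [1 − Φ(0.5/0.354)] = 2 × [1 − Φ(1.414)] ≈ 16%.

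**3. What a systematic imbalance does.** Suppose Cohort 2 starts 0.5 SD higher (0.5 × 3.9 = 1.95 TILs) and lirilumab has no effect. The spurious difference is ρ × 1.95. The rejection rate of the rank-sum test is approximately 1 − Φ(1.2816 − √(3/π) × ρ × 0.5/0.354).

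| ρ | Spurious difference (TILs per 100) | Error, formula | Error, simulation | Adjusted tests |
|---|---|---|---|---|
| 0.3 | 0.6 | 19% | 19–20% | about 10% |
| 0.5 | 1.0 | 28% | 27–28% | about 10% |
| 0.7 | 1.4 | 38% | 36–37% | about 10% |

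The simulation column gives the range across simulation runs. The adjusted tests are a Quade rank ANCOVA and a linear ANCOVA on TURBT density.

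**4. Power at 0.80 SD with balanced baselines (simulation).**

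| ρ | Rank-sum as planned | Quade rank ANCOVA | Linear ANCOVA |
|---|---|---|---|
| 0 | 81% | 80% | 82% |
| 0.3 | 81% | 82–83% | 85% |
| 0.5 | 81% | 87% | 89–90% |
| 0.7 | 81% | 94–95% | 96% |

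**5. An indirect hint about ρ.** The protocol's signed-rank powers of 81% and 98% are close to what an SD of 3.9 for the *change* gives: a noncentral t with effect 3.0/3.9 gives 80% for 12 patients and 98% for 24. If density and its change share one SD and the pre and post variances are equal, then 2(1 − ρ) = 1, so ρ = 0.5. This is an inference from the planning figures, not a measured correlation.

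**6. Would the raw change score do instead?** A rank-sum test on the change has power of about 60%, 71%, 81% and 93% at ρ = 0, 0.3, 0.5 and 0.7. It loses power below ρ = 0.5. It also over-corrects: with Cohort 2 starting 0.5 SD higher, its error is only about 2–3% at ρ = 0.3 to 0.7. A covariate is the better use of the baseline value.

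**The case against.** Four points can fairly be made for the plan.

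- **The baseline value is not ignored throughout.** A reader might infer that this test is the trial's only estimate of what lirilumab adds on TIL density, or that TURBT density goes unused. The documents do not support that. Percent change from TURBT is compared between cohorts as a secondary endpoint, which ranks above this exploratory test. That comparison is no substitute, however. It is undefined when TURBT density is zero, unstable when it is small, and does not adjust the density comparison.
- **The comparison is exploratory.** The trial is a Phase Ib study with a safety primary endpoint, and no decision rule rests on this test. That limits the consequence, and the point is an improvement rather than a flaw in the trial's main result.
- **Error is not inflated on average.** Given a one-SE chance imbalance favouring Cohort 2, the 10% error becomes 1 − Φ((1.2816 − ρ)/√(1 − ρ²)) = 15%, 18% or 21% at ρ = 0.3, 0.5 or 0.7. A reader might take these as general inflation. The same imbalance in the other direction gives 5%, 2% or 0.3%, and averaged over chance imbalance the test holds its 10%. Average inflation needs a systematic difference, and the documents give neither evidence for one nor its size.
- **The power gain rests on an assumed correlation.** Near ρ = 0 there is none.

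What remains is that sequential, non-randomised allocation leaves a systematic difference possible, and the planned test offers no protection against it although the needed variable is already to be collected.

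**Conclusion.** The point holds for this one comparison. The 82% power is correct and the unadjusted test is valid on average under chance imbalance. It is exposed to any systematic baseline difference: at 0.5 SD in favour of Cohort 2, the one-sided 10% error about doubles at ρ = 0.3 and reaches 36–37% at ρ = 0.7, while adjusted tests hold near 10%. At the implied ρ of 0.5, adjustment is worth about 6 to 8 points of power.

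These sizes depend on the assumed correlations, on the 0.5 SD imbalance being illustrative, on normal data with equal variances, and on 12 and 24 complete pairs. The last may not be met. The density needs at least 100 tumor cells per field, so a patient with no residual tumor may have no cystectomy value. That shrinks the analysed number for either method.

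Nor should a reader infer that an adjusted result would isolate lirilumab's effect. Adjustment removes confounding by baseline density only, and other differences between sequentially enrolled cohorts remain.

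**What to change.** Amend protocol 13.2.2.1 and SAP 7.4.2.1, 7.4.3.1 and 7.7.1 as follows, keeping the exploratory label in each place.

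1. Main test: Quade rank ANCOVA of cystectomy density with TURBT density as covariate, at the same one-sided 0.1 level.
2. Estimate: adjusted cohort difference with a confidence interval from a linear model with TURBT density as covariate. Quade's test does not itself supply this. If the model is on the log scale, state the rule for zero densities in advance.
3. Sensitivity: the unadjusted rank-sum test as now planned.
4. Add two sentences: that adjustment deals with baseline density only, and that patients without an evaluable cystectomy density are not in this analysis, with the analysed number reported per cohort.

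The cost is one degree of freedom, a short change of wording and a few lines of code. No new data are needed. It should be settled before database lock.
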